APPENDIX B: DATA DICTIONARY

Pre-operative Data Fields	Required data (definition / comment)
1. Patient age	Years (Whole years at the time of operation)
2. Patient sex at birth	Male / Female
3. ASA grade	I / II / III / IV / V (Appendix D for definitions)
4. Body Mass Index (BMI in kg/m ²)	Underweight BMI Below 18.5 / Normal weight BMI 18.5-24.9 / Pre-obesity BMI 25.0-29.9 / Obesity class I BMI 30.0-34.9 / Obesity class II BMI 35.0-39.9 / Obesity class III BMI 40+
5. Clinical Frailty Scale	1 / 2 / 3 / 4 / 5 / 6 / 7 / 8 / 9 (Appendix D for definitions)
6. Comorbidities (Select all that apply)	
Myocardial Infraction (MI) / Congestive Heart Failure (CHF) / Peripheral Vascular Disease (PVD) Cerebrovascular Accident (CVA) or Transient Ischaemic Attack (TIA) / Dementia / Chronic Obstructive Pulmonary Disease (COPD) / Connective Tissue Disease (CTD) Peptic Ulcer Disease (PUD) / Hemiplegia / Leukaemia / Lymphoma / Human Immunodeficiency Virus (HIV) or Acquired Immunodeficiency Syndrome (AIDS) / Hypertension / Inflammatory Bowel Disease (IBD) / Diabetes Mellitus (Type 1 or Type 2). If yes: Diet-Controlled / Medication (non-insulin) controlled / Insulin-controlled Solid Tumour. If yes: Localised / Metastatic Liver Disease. If yes: Mild / Moderate to Severe Chronic Kidney Disease (CKD). If yes: Stage I / II / IIIa / IIIb / IV / V None of the Above
 
Definitions:
 
 eGFR for CKD stages: I ≥ 90; II = 60-90; IIIa = 45-59; IIIb = 30-44; IV = 15-29; V <15 Definitions for Liver Disease: Mild defined as chronic hepatitis or cirrhosis without portal hypertension; Moderate defined as cirrhosis and portal hypertension but no variceal bleeding history; Severe defined as cirrhosis and portal hypertension with variceal bleeding history.
7. History of acute cholecystitis or cholangitis	Yes / No
8. Number of admissions with biliary symptoms in previous 12 months prior to surgery	Number of admissions excluding the current one
9. Preoperative imaging (Select all that apply)	Yes / Unknown / No (Not available / Not indicated / Patient declined) for each of the following: USS / CT / ERCP / MRCP / Endoscopic Ultrasound (EUS) / Hepatobiliary IminoDiacetic Acid (HIDA)
10. Preoperative imaging findings*	
*Only for USS / CT / MRCP, what are the findings (tick all that apply): Gallstones Thick-walled Gallbladder (≥3mm or reported as thick walled) Pericholecystic fluid CBD stones Dilated CBD. If yes: CBD diameter (record in mm, to one decimal)

11. Days between first biliary symptom onset and admission	Number of days (Whole number, day 0 is same day of first symptom onset)

12. Days between diagnosis and decision to operate	
Number of days (Whole number, day 0 is same day of diagnosis)
 
Guide for decision to operate day:
 
 For elective cases this should be the day the patient was seen in the outpatient clinic. For delayed cases this is the day the patient was LAST discharged from hospital with biliary disease. For emergency cases this should be the day the decision was made to perform an acute cholecystectomy in that emergency admission. If the patient was previously on an elective waiting list for surgery, please still use the date it was decided to perform the operation as an emergency.
13. Days between decision to operate and surgery performed	
Number of days (Whole number, day 0 is same day as surgery)

14. Urgency of surgery (Appendix D for definitions)	
Elective Delayed Emergency. If yes: Was the patient already on the elective waiting list for surgery? (Yes / No)

15. Indication for surgery (Appendix D for definitions)	
Acute calculous cholecystitis. If yes: Tokyo grade: I / II / III (Was the Tokyo grade documented in patient notes: Yes / No) Biliary colic Acalculous cholecystitis Chronic calculous cholecystitis Common Bile Duct (CBD) stone Gallbladder polyp Dyskinesia Gallstone pancreatitis. If yes: Atlanta criteria: mild / moderate / severe (Was the Atlanta criteria documented in patient notes: Yes / No)

Intra-operative Data Fields	Required data (definition / comment)
1. Mode of Anaesthesia* (Select all that apply)	
Local (subcutaneous / intraperitoneal) Regional (spine-related / regional nerve block) Sedation (e.g., midazolam) General Inhaled (sevoflurane / halothane / desflurane / Nitric Oxide (N2O) / isoflurane) Total Intravenous Volatile Anaesthetic (TIVA) *This refers to the anaesthetic used during the operation and NOT as induction agents

2. Intraoperative antibiotics*	
Yes (Prophylactic / Intraoperative spillage / Cholecystitis) / No *Defined as administration of antibiotics at least 30 minutes prior to skin incision to end of operation

3. Primary operator	
Consultant or attending Senior trainee (i.e., senior registrar or resident with >4 years surgical training/residency) Junior trainee (i.e., junior registrar or resident with ≤ 4 years surgical training/residency) Non-surgeon (e.g., medical practitioner or nurse)
 
If Consultant: What specialty? (General / Oesophago-gastric (OG) / HPB / Colorectal / Breast / Vascular / Other) If Trainee: Was this a training operation? (Yes / No). Was a consultant present? (Yes / No) If any: Number of cholecystectomies performed prior to this procedure: 0-50 / 51-100 / 101-200 / >200

4. Operative approach	
Open / Open conversion / Laparoscopic (Standard / Single Incision Laparoscopic Surgery (SILS)) / Robotic (Standard / SILS)
 
 If open, why: No laparoscopic equipment / Surgeon not trained in laparoscopy / Laparoscopy equipment broken / Multiple previous surgery / Disease severity. If open conversion, why: Suboptimal view / Adhesions / Not able to safely dissect CVS / Suspected bile duct injury / Patient unable to tolerate pneumoperitoneum / Bleeding / Bowel injury / Laparoscopic or robotic equipment failure / Suspected or actual cholecystoduodenal or cholecystocolonic fistula. If laparoscopic or robotic: was this gasless (Yes / No), were reusable equipment used? (Yes / No).
5. Intra-operative difficulty score – this is for minimally invasive surgery	
I / II / III / IV / V (Nassar Grade: Appendix D for definitions)

6. Was the Critical View of Safety (CVS) obtained (all three) – this is for minimally invasive surgery	
Yes / No If no, which criteria was met: 1) Clearing fat and fibrous tissue from the hepatocystic triangle.

	2) The lower third of the gallbladder being cleared from the cystic plate. 3) Only two structures are attached to the gallbladder.
7. Was there a time-out to verify CVS	Yes / No Defined as a momentary pause that what one is seeing is likely the correct anatomy
8. Operation performed	Standard total cholecystectomy Total cholecystectomy by the fundus-first (top down) approach Subtotal cholecystectomy (reconstituting / fenestrated) Not performed (diagnostic laparoscopy / cholecystostomy) Definitions of subtotal cholecystectomy: 
 Fenestrated: does not occlude the gallbladder but may suture the cystic duct internally Reconstituting: closes off the lower end of the gallbladder, creating a remnant gallbladder
9. Abdominal drain insertion	Yes / No
10. Anatomical Biliary variant	Yes / No
11. Intraoperative CBD Assessment	Intraoperative cholangiogram (IOC) / Incisionless fluorescent cholangiography/ Laparoscopic ultrasound / Intraoperative ERCP If yes to any of the above: 
 Decision: Selective / Routine. If selective, state Indication: Raised liver function test / Concern of a bile duct injury / pre-operative imaging suggestive of CBD stone Findings: Stone / No stone. If stone, tick all that apply for management: Flushing with saline and smooth muscle relaxant / Fogarty catheter trawl / Basket retrieval / Choledochoscope / No intraoperative treatment attempted
12. Common Bile Duct exploration	Yes (Trancystic / Choledochotomy) / No If Choledochotomy then select closure: Primary closure / T-tube
13. Operative contamination	Clean (Gastrointestinal (GI) and genitourinary (GU) tract not entered) Clean-Contaminated (GI or GU tracts entered but no gross contamination) Contaminated (GI or GU tracts entered with gross spillage or major break in sterile technique) Dirty (There is already contamination prior to operation, e.g., faeces or bile).
14. Intraoperative complications - excluding bile duct injury (BDI) (Select all that apply)	Bile spilt / Stones Spilt / Bleeding / Major vascular injury / Bowel injury
15. Were reusable gowns used in this procedure?	Yes (All scrubbed staff/ some scrubbed staff) / No
16. Were reusable drapes used in this procedure?	Yes / No
30-day Outcomes	Required data (definition / comment)
1. Highest 30-day Clavien-Dindo (CD) Grade	0 / I / II / IIIa / IIIb / IVa / IVb / V (Appendix D for definitions) If CD IIIa: Radiological drainage (yes / No) If CD IIIb: Re-laparoscopy (yes / No) If CD V (death): please indicate time from index cholecystectomy to death: number of days (whole number, 0 = same day)
2. Unplanned critical care admission - where critical care admission was not part of pre-operative plan	Yes / No If yes, please indicate length of stay in critical care: number of days (whole number)
3. Unplanned Re-imaging - where imaging in post-operative period (e.g.,	Yes / No If yes then tick all that apply: USS / CT / MRI / ERCP

CT, MRCP) was not part of pre-operative plan
	

4. 30-day postoperative complications (Select all that apply)
	
Surgical site infection (CD Grade* 0 / I / II / IIIa / IIIb / IVa / IVb / V) Postoperative pulmonary complications (CD Grade* 0 / I / II / IIIa / IIIb / IVa / IVb / V) Bile leak (CD Grade* 0 / I / II / IIIa / IIIb / IVa / IVb / V) Bleeding (CD Grade* 0 / I / II / IIIa / IIIb / IVa / IVb / V) Intra-abdominal collection (CD Grade* 0 / I / II / IIIa / IIIb / IVa / IVb / V) Acute pancreatitis (CD Grade* 0 / I / II / IIIa / IIIb / IVa / IVb / V) *For all of the above, please indicate the Clavien-Dindo grade associated with that complication

5. Length of stay
	
Whole number of days (Where discharge < 23 hours, enter 0. If the patient has not been discharged prior to the end of 30-day follow-up, enter '31')

6. Unplanned readmission within 30 days
	
Yes (Length of stay) / No

Bile Duct Injury (BDI) data fields
	
Required data (definition / comment)

1. BDI identified within 30-days of index cholecystectomy
	
Yes / No If yes: please fill in the rest of the data points below. If No: Was BDI identified within one-year of index cholecystectomy: Yes / No (if yes, then please fill in the rest of the data points below)

2. Presentation of BDI
	
Intraoperatively / Controlled bile leak from surgically placed abdominal drain / Abdominal pain due to uncontrolled bile leak / Obstructive jaundice or cholangitis / Intra-abdominal abscess or biloma

3. Days from index cholecystectomy to diagnosis
	
Number of days (0 = intraoperatively)

4. Bile duct injury grade
	
A / B / C / D / E1 / E2 / E3 / E4 / E5 (Strasberg Injury Grade: Appendix D for definition)

5. Concomitant vascular injury
	
Yes (Right hepatic artery / Common hepatic artery / Main portal vein / Right portal vein) / No


6. Imaging modality to investigate and confirm BDI
	
On-table cholangiography (OTC) / USS / MRCP / CT / ERCP / Percutaneous transhepatic cholangiography (PTC) / Nuclear medicine scan (e.g. Functional liver scan) / Tubogram / None

7. Discussion with a specialist HPB centre
	
Yes / No / Not required (Injury occurred at specialist HPB centre) If yes:
 
 Transferred to specialist HPB centre: Yes / No Time from injury to referral: number of days (whole number)

8. Management of Bile duct injury (Select all that apply)
	
Non-surgery (ERCP only / ERCP and stent / PTC) / Surgery (washout only / repair) If any of the above:
 
 Time after index cholecystectomy: number of days (Whole number, day of index cholecystectomy = day 0) 
If surgical repair:
 
 Specialty of surgeon performing Bile duct injury repair: HPB surgeon / UGI surgeon / General surgeon Method of repair: Roux-en-Y Hepaticojejunostomy / CBD repair without T-tube / CBD repair with T-tube / CBD end to end anastomosis / Hepaticoduodenostomy Vascular repair: Yes / No One-year complications: Stricture formation / Cholangitis / anastomotic leakage / intra-abdominal abscess or biloma / re-repair. If yes to any, time from repair to complication: number of days (Whole number, day of repair = day 0)

	Stricture definition: defined as a clinically relevant stricture leading to either jaundice, significant alterations of the liver function tests, cirrhosis or reoccurring cholangitis requiring radiological/surgical intervention or a liver failure related death
Histology data fields	Required data (definition / comment)
1. Postoperative histology	
Not sent for examination / Sent for examination
 
If sent for examination, please complete:
 
 • Indication: Routine / Selective • Time from index cholecystectomy to histology result: Number of days (whole number) • Result: Benign / Malignant 
If Malignant, please complete the rest of the data points below

2. Staging investigations after index cholecystectomy (select all that apply)	
CT thorax abdomen pelvis / MRI liver / PET-CT / Staging laparoscopy
 
For any of the above, please indicate time from histology result to staging investigation: number of days (whole number)

3. TNM grade (AJCC 8th edition) (Appendix D for definition)	
T category: Tis / T1a (lamina propria) / T1b (muscularis) / T2a (peritoneal side) / T2b (hepatic side) / T3 / T4
 
N category: N0 / N1 (1-3 nodes) / N2 (>3 nodes)
 
M category: M0 / M1

4. Discussed at MDT	Yes / No
5. Adjuvant treatment	No / Chemotherapy / Radiotherapy
6. Revisional surgery completed	
Yes / No (not required) / No (unresectable tumour)
 
 • If yes, type of surgery (select all that apply): Liver resection (liver bed / one segment / two segments/ ≥ 3 segments) / bile duct resection / lymph node dissection • If yes, time from histology result to revisional surgery: Number of days (whole number)
7. Pathology results if revisional surgery	
Resection margin status: R0 / R1 / R2
 
Lymphovascular invasion: Yes / No
 
Perineural invasion: Yes / No
 
Resection margin definition: R0 = microscopically negative for residual tumor; R1 = microscopically margins still demonstrate the presence of tumor; R2 = macroscopically-visible disease remains post-surgery.

8. Recurrence on imaging at one year	
Yes / No
 
If yes, time from surgery to recurrence: number of days (whole number)

One-year Outcomes	Required data (definition / comment)
1. Highest one-year Clavien-Dindo (CD) Grade	
0 / I / II / IIIa / IIIb / IVa / IVb / V
 
If CD IIIa: Radiological drainage (yes / No)
 
If CD IV: Re-laparoscopy (yes / No)
 
If CD V (death): please indicate time from index cholecystectomy to death: number of days (whole number)

2. Readmissions	Total number of readmissions

3. One-year complications
(Select all that apply)

Surgical site infection (CD Grade* 0 / I / II / IIIa / IIIb / IVa / IVb / V)

Postoperative pulmonary complications (CD Grade* 0 / I / II / IIIa / IIIb / IVa / IVb / V)

Bile leak (CD Grade* 0 / I / II / IIIa / IIIb / IVa / IVb / V)

Biliary stricture (CD Grade* 0 / I / II / IIIa / IIIb / IVa / IVb / V)

Bleeding (CD Grade* 0 / I / II / IIIa / IIIb / IVa / IVb / V)

Intra-abdominal collection (CD Grade* 0 / I / II / IIIa / IIIb / IVa / IVb / V)

Acute pancreatitis (CD Grade* 0 / I / II / IIIa / IIIb / IVa / IVb / V)

*For all of the above, please indicate the Clavien-Dindo grade associated with that complication

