2. To assess adverse events following cholecystectomy (e.g., bile duct injury) and their management.
3. To analyse rates and outcomes of unsuspected gallbladder cancer.
4. To evaluate the global variation in the availability of cholecystectomy services and training amongst included hospitals.
5. To assess sustainable practices in laparoscopic cholecystectomy globally.

AUDIT STANDARDS

Pre-operative

1. **Interventional radiology service:** There should be 24-hour access to interventional radiology to support the delivery of an emergency HPB service [11].
2. **Risk Stratification:** For patients with acute cholecystitis, surgeons may use the Tokyo Guidelines 18 (TG18) [8].
3. **Timing of surgery:** In patients presenting with acute cholecystitis, the optimal timing for cholecystectomy is within 48 hours, and no more than 10 days from symptom appearance [7].

Intra-operative

1. **Critical Safety View (CVS):** The use of the CVS during laparoscopic cholecystectomy (achieving all 3 components – Figure 1) is the recommended approach to correctly identify relevant anatomy and minimize the risk of bile duct injuries [7,8]:
 - I. **Clearance of the hepatocystic triangle:** The HC triangle should be cleared of all the fibro-fatty and soft areolar tissue.
 - II. **Exposure of the lower cystic plate:** The gallbladder should be separated from its liver bed to expose at least the lower third of the cystic plate.
 - III. **Only two tubular structures should be seen entering the gallbladder:** the cystic duct and the cystic artery.

[figure not shown]

Figure 1: Photographs showing the critical view of safety.

2. **Intraoperative imaging:** in patients with uncertainty of biliary anatomy or suspicion of bile duct injury, intraoperative imaging (e.g. cholangiogram, laparoscopic ultrasound and incisionless cholangiography with fluorescence) may help delineate relevant anatomy, detect bile duct stones, and decrease the risk of bile duct injury [7,8,12].
3. **Bailout Procedures:** When CVS cannot be achieved and the biliary anatomy cannot be clearly defined by other methods (e.g. imaging) during laparoscopic cholecystectomy, surgeons should

consider a bailout procedure (e.g. subtotal cholecystectomy or total cholecystectomy by the fundus-first (top down) approach) [7].

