4. **Antibiotic use:** Antibiotics are not required in low risk patients undergoing laparoscopic cholecystectomy, but may reduce the incidence of wound infection in high risk patients (age > 60 years, the presence of diabetes, acute colic within 30 days of operation, jaundice, acute cholecystitis, or cholangitis) [12].
5. **Use of drains:** drains are not needed after elective laparoscopic cholecystectomy and their use may increase complication rates; however, they may be useful in complicated cases particularly if choledochotomy is performed [12].
6. **Bile Duct Injury (BDI):**
 - a. If major BDI occur, outcomes are improved by early recognition and immediate referral to experienced hepatobiliary specialists for further treatment before any repair is attempted by the primary surgeon, unless the primary surgeon has significant experience in biliary reconstruction [7,8,12].
 - b. If considering all types of BDIs, rates are 0.4% and 0.8% for elective and emergency settings, respectively [7].
 - c. It is recommend knowing Strasberg's classification, which remains the most commonly used classification for BDIs [7].

Post-operative

1. **30-day readmission:** rate should be <10% [11].
2. **Critical care:** There should be access to critical care beds (both level 2 and level 3) with on-site renal support [11].

OVERVIEW OF STUDY DESIGN

GECKO is a prospective, international, multicentre, observational cohort study delivered by GlobalSurg Collaborative. This will be on consecutive patients undergoing cholecystectomy, between 31st July 2023 to 19th November 2023, with follow-up at 30-day and one-year postoperatively. Mini-teams of up to five collaborators ([see page 17](#)) per 14-day data collection period will prospectively collect data at each participating centre.

GLOBALSURG COLLABORATIVE

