Validation by primary data collection teams:

- Follow-up methodology at patient level: all hospitals will self-report the methods used to determine 30-day outcomes.
- Patient identification methodology: all hospitals will self-report the methods used to identify patients who fulfil the inclusion criteria.

Validation by independent teams:

- Case ascertainment: hospital records will be reviewed to identify patients fulfilling the inclusion criteria within a 2-week data collection period and comparing this to the actual number of cases submitted. This will be performed by individuals not involved in collecting the primary data. By comparing samples, a quantitative estimate of case ascertainment will be produced by the central data team.
- Data accuracy: a subset of collected variables will be validated by individuals who are independent of the primary data collection process. Following the “case ascertainment” stage, validators will be asked to provide data for a subset of variables, two patient variables, two operation variables, and two outcome measures.

Project Team Structure

Each registered centre must have a supervising consultant/attending to ensure adequate data quality. In the case that the hospital lead is a registrar/resident then they must recruit a consultant/attending to supervise the study. The hospital lead should also ensure that they recruit independent data validators (registrars/residents or consultants/attendings) to perform the data validation outlined in the section above.

For data collection, the hospital lead should recruit a “mini-team” of up to five local collaborators for each data collection period (**Table 1; page 15**). Medical students, doctors (non registrars/residents or consultants/attendings) and nurses can act as local collaborators and their participation is encouraged. The same “mini-team” can cover different time periods at each hospital if they wish to. Each team should include at least one qualified doctor to provide additional local support for participating medical students or nurses. Additional collaborators can be recruited to aid one-year follow-up data collection once the follow-up period begins (31st Jul 2024). A detailed specification of each role can be found below (see **pages 23-24**).

STATISTICAL CONSIDERATIONS

Primary Outcome Measure

The primary endpoint of this study is the compliance to pre-, intra-, and post-operative audit standards (see pages 9-10).

Secondary Outcome Measures

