6. **Living With Moderate Frailty:** People need help with all outside activities and housekeeping. Inside often have problems with stairs, need help with bathing, and may need minimal assistance with dressing.
7. **Living With Severe Frailty:** Completely dependent for cognitive and physical personal care. However, they seem stable and not at high risk of dying (within six months).
8. **Living with Very Severe Frailty:** Completely dependent for personal care and approaching end of life. Typically, they could not recover even from minor illnesses.
9. **Terminally Ill:** Approaching the end of life. This category applies to people with a life expectancy of under six months who are not otherwise living with severe frailty.

Indication for Surgery

Indication	Definition
Biliary colic	The presence of colicky right upper quadrant pain associated with gallstones or sludge on an USS, but no signs of acute cholecystitis [23]
Acute calculous cholecystitis	Clinical (right upper quadrant pain, with or without fever, WCC > 11 × 10 ⁹ /l) OR ultrasound evidence (thick walled gallbladder (≥ 3mm), OR USS tenderness over the gallbladder, the presence of gallstones) [23,24]
Acute acalculous cholecystitis	Clinical OR ultrasound evidence (thick walled gallbladder and/or pericholecystitis, USS tenderness over the gallbladder) in the absence of gallstones [23]
Chronic calculous cholecystitis	Previous clinical or ultrasound evidence (thick walled gallbladder and/or pericholecystitis, OR USS tenderness over the gallbladder OR the presence of gallstones) of cholecystitis [23]
Common bile duct stone	Common bile duct stones, as confirmed by before or at the time of surgery
Gallbladder polyp	Hyperechoic lesions on USS imaging which have no acoustic shadow and do not move with positional changes, with no overt features of malignancy [25]
Dyskinesia	Biliary like abdominal pain, occurring in a normal appearing gallbladder with a functional HIDA scan showing an abnormal gallbladder ejection fraction of less than 40% [26,27]

Tokyo Guidelines 2018 for Grading of Acute Cholecystitis

Tokyo guidelines 2018 grading [24] are listed below:

- **Grade I (mild):** No organ dysfunction and mild inflammatory changes in the gallbladder.
- **Grade II (moderate):**
 - Elevated WBC count (>18,000/mm³)
 - Palpable tender mass in the right upper abdominal quadrant
 - Duration of complaints >72 hours

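### The Tokyo grade is collected only for acute calculous cholecystitis, so acalculous cases cannot be scored on the TG18 audit standard; the indication item also overlaps and has no stated selection rule

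*Protocol*

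**What the plan says.** Under Statistical Considerations, Primary Outcome Measure: "The primary endpoint of this study is the compliance to pre-, intra-, and post-operative audit standards". Two pre-operative audit standards are defined for acute cholecystitis:

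- Standard 2, risk stratification: "For patients with acute cholecystitis, surgeons may use the Tokyo Guidelines 18 (TG18".
- Standard 3, timing: "In patients presenting with acute cholecystitis, the optimal timing for cholecystectomy is within 48 hours, and no more than 10 days from symptom appearance".

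Neither is limited to calculous disease. Acute cholecystitis is identified through Appendix B, pre-operative item 15, headed "15. Indication for surgery (Appendix D for definitions". Its first option is acute calculous cholecystitis, with the sub-items "Tokyo grade: I / II / III (Was the Tokyo grade documented in patient notes: Yes / No". The remaining options are "Biliary colic Acalculous cholecystitis Chronic calculous cholecystitis Common Bile Duct (CBD) stone Gallbladder polyp Dyskinesia Gallstone pancreatitis", none with a Tokyo sub-item. The case report form in Appendix A has the same nesting. The indication table in Appendix D has a separate row for acute acalculous cholecystitis, and defines the duct-stone indication as "Common bile duct stones, as confirmed by before or at the time of surgery".

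**The concern.** A compliance rate needs a denominator (who the standard applies to) and a numerator (who met it). For standard 2 the denominator includes acalculous patients, but the forms never ask the numerator question for them. For standards 2 and 3 together, the denominator depends on which indication box is ticked, and the protocol does not say whether one or several may be ticked when a patient fits more than one.

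At stake is whether two components of the primary endpoint mean the same thing at every site. The protocol anticipates around 500 centres. If some collectors code a patient with acute cholecystitis and a duct stone under one heading and some under the other, part of the apparent variation between centres would reflect coding.

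**Working it through.** No figure in the protocol is contested, so the check is mainly a comparison of sections.

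**1. Can acalculous cases be scored on standard 2?**

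- Audit Standards, pre-operative 2: applies to acute cholecystitis, without a calculous restriction.
- Appendix D, indication table: names an acute acalculous form, so these patients have acute cholecystitis by the protocol's own definitions. The two forms drop the word acute from the option label but keep it as a separate code.
- Appendix A and Appendix B item 15: the grade and the documentation question open only under the calculous option.
- Reconstruction: the TG18 criteria in Appendix D rest on white cell count, a palpable mass, symptom duration, local inflammation and organ dysfunction. The pre-operative fields hold no white cell count or organ-function values. Whether the surgeon recorded a grade in the notes cannot be inferred from any other field.

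Result: no acalculous case can be scored on standard 2.

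**2. Do acalculous cases also drop out of standard 3?**

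No. They have their own code, and the three interval items (Appendix B, pre-operative items 11 to 13) are recorded for every patient. A timing denominator built from both codes can be formed from the data as collected.

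**3. Are the options exclusive, and may several be chosen?**

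- The duct-stone definition does not exclude concurrent acute cholecystitis.
- Gallstone pancreatitis has no row in the Appendix D indication table, so nothing separates it from coexisting cholecystitis.
- No order of precedence is given.
- Item 15 has no multi-select mark in Appendix A or Appendix B. Three other fields have the mark in one form and lack it in the other: intraoperative duct assessment (marked in Appendix A only), intraoperative complications and staging investigations (both marked in Appendix B only). A missing mark is therefore weak evidence of single choice, although item 15 lacks it in both places.

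The two possible readings give:

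| Item 15 run as | Acute calculous cholecystitis with duct stone or pancreatitis | Acalculous |
|---|---|---|
| Multi-select, all applicable boxes ticked | In both denominators, Tokyo fields open | Standard 3 only |
| Single-choice, coded as duct stone or pancreatitis | Out of both denominators, Tokyo fields closed | Standard 3 only |

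**4. What would single-choice coding do to a compliance rate?**

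Let m be the share of true acute cholecystitis coded elsewhere, and c_in and c_out the compliance in counted and missed cases. Then

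reported − true = c_in − [(1 − m) × c_in + m × c_out] = m × (c_in − c_out).

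The protocol gives none of these inputs. Purely as assumptions, take m from 5% to 20% and an absolute difference from 10 to 30 percentage points:

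- low end: 0.05 × 10 = 0.5 points;
- high end: 0.20 × 30 = 6 points.

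The sign depends on whether missed cases comply less or more often than counted ones, which the protocol does not show.

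**The case against.** The strongest reply is that single choice is stated nowhere. The protocol marks multi-select fields inconsistently, the printed layout of this part of the case report form was disturbed when the text was read from PDF, and the REDCap field type is not shown. If several boxes may be ticked, patients with acute calculous cholecystitis plus a duct stone or pancreatitis stay in both denominators. That stands, and it makes this half of the point conditional.

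Other fields also carry information: imaging findings, urgency, history of acute cholecystitis or cholangitis, and cholecystitis as the reason for antibiotics. This recovery is real but partial. The history item does not record the current indication, and the antibiotic reason exists only where antibiotics were given. None of these fields supplies a Tokyo grade.

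Standard 2 is permissive in wording, and the protocol says some standards will not be treated as mandatory or as definitive measures of quality. This limits the consequence. Compliance with the standards nevertheless remains the declared primary endpoint. Deriving denominators can be left to a statistical analysis plan, but collecting the grade cannot.

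Three stronger readings are tempting and are not supported:

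- A reader might infer that acalculous cases are lost from the timing standard as well. Step 2 shows they are not.
- A reader might infer that timing compliance is overstated, because patients with duct stones or pancreatitis plausibly wait longer. The protocol contains no data on this.
- A reader might count the absence of an 'other' indication as part of the same fault. No effect of that absence on the acute-cholecystitis standards can be shown.

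**Conclusion.** Upheld in two parts of different strength.

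**Firm:** acalculous cases fall within standard 2 as worded but cannot be scored on it. The loss is complete for that subgroup on that standard and cannot be repaired at analysis. The subgroup's size is not given, so the effect on the overall standard 2 rate is unknown.

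**Conditional:** item 15 has overlapping options and no written selection rule. Only if it is run as single-choice does acute cholecystitis coded as duct stone or gallstone pancreatitis leave the TG18 and timing denominators. The 0.5 to 6 point range is an illustration under assumed inputs. Neither the size nor the direction of a bias follows from the protocol.

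The change should be made because it is cheap and concerns a component of the primary endpoint.

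**What to change.** 1. Open the Tokyo grade and the documented-in-notes question whenever acute calculous or acute acalculous cholecystitis is ticked, on the case report form, in Appendix B and in REDCap.
2. Mark item 15 as multi-select in both forms. If a single label is wanted for tables, add a main-indication sub-item.
3. Define the denominators of standards 2 and 3 as any record with either acute code ticked.
4. If the Tokyo items are not extended, state that standard 2 is assessed in calculous disease only.

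The cost is a small change of field type and branching in REDCap and on the case report form. With several indications allowed, the categories no longer sum to 100% unless the main-indication sub-item is used.
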